For healthcare utilization outcomes (e.g., ED visits), assuming a standard deviation of 3 for the number of ED visits for asthma per person per year and nearly 90% power, a sample size of 97 per arm will allow us to detect a difference of 1.4 in annual number of ED visits between the two groups at the significance level of 0.05 (2-sided).

For this protocol, we are requesting approval of a sample size of 5,000. This includes approximately 4,000 possible screen/fails. This will also allow us to enroll slightly more than 300 without submitting an amendment to the IRB. The primary reason for enrolling more than 300 would be an unexpectedly high drop-out rate.

Provide a description of your plan for data analysis. State the types of comparisons you plan (e.g. comparison of means, comparison of proportions, regressions, analysis of variance). Which is the PRIMARY comparison/analysis? How will the analyses proposed relate to the primary purposes of your study?

All analyses will be performed according to treatment assignment, and all available data will be included in the evaluations, regardless of whether or not the subjects discontinue the assigned treatment (modified intention-to-treat analysis). Bivariate associations will be examined using Student t-tests and chi-square tests, as appropriate. Linear and logistic regression models with generalized estimating equation variance estimates will be used to evaluate differences among treatment groups for continuous or dichotomous outcomes, respectively. Unadjusted analysis will be performed as the primary results. If baseline covariate imbalance is detected, the analysis will adjust for imbalanced covariates. Subgroup analyses will be performed in pre-specified groups defined by age, sex, race, and asthma severity. P values of less than 0.05 (2-sided) will be considered statistically significant. P values will not be adjusted for multiple comparisons. Analyses will be carried out using the current versions of SAS, Stata, or R.

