#### Statistical Analysis

Summary statistics were calculated for the entire cohort, stratified by treatment group. Baseline demographics, clinical outcomes, and environmental exposures were summarized by means (standard deviations), medians (ranges), or frequencies (percentages). Baseline characteristics were compared between treatment groups using an independent two-sample t-test, Wilcoxon rank sum tests, chi-square tests, or Fisher's exact test. Baseline summary statistics were also compared between patients who completed the study (N=193) and those who did not (N=71). All hypothesis tests were two-sided and assessed at the 0.05 level of significance.

Primary Outcome Analyses. The primary outcome measures of interest for this study were the ACT™, MiniAQLQ, and ED visits in the previous 12 months at exit. The ACT™ score is the sum of the scores of the 5 items included in the questionnaire. If any of the five items was missing a response, then no score was computed. The MiniAQLQ scores were computed using two methods, per scoring recommendations. The MiniAQLQ was first computed as the average of the scores for the 15 items. If any of the 15 items was missing a response, then no score was calculated. Alternatively, the MiniAQLQ was also scored if 2 or fewer responses were missing by replacing the missing responses with the worst score (regression to the null). After replacement, the MiniAQLQ was then calculated as the average of the scores for the 15 items. The alternative MiniAQLQ was used as the primary measure for asthma quality of life. ED utilization was measured by the frequency of visits to an ED during the 12-month period prior to the exit visit.

The initial analysis of the outcome measures used an independent, two-sample, two-sided t-test, assuming equal variances, to compare the mean ACT™ scores, MiniAQLQ scores, and ED visits over the previous 12 months between treatment groups at study exit. The equal variance assumption was tested using the F test at the .05 level and, if rejected, Welch's t-test approximation was used as alternative analysis. Approximate normality was assessed by using histograms, box-plots, skewness, kurtosis, and the Shapiro-Wilks test. Departures from

normality were addressed by using nonparametric analytic methods or data transformation.

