In addition to the t-test, the Wilcoxon rank-sum test and Fisher's exact test were used to compare treatment groups for the ED visits outcome measure. The Wilcoxon rank-sum test was used to test for significant differences in the location of the distribution of ED visits between treatment groups. The outcome measure was also redefined as a binary outcome to compare the proportion of participants who had at least one visit to the ED by treatment group using the Fisher's exact test. Other outcome measures were similarly compared between treatment groups using t-tests, Wilcoxon rank-sum tests, chi-square tests, or Fisher's exact tests.

To assess between-group differences for the primary outcome measures, we calculated the raw mean difference (MD) for the continuous variables, ACT™ and MiniAQLQ; and the odds ratio (OR) for the binary variable, ED visits.

Exploratory Analyses. Data on ACT™, MiniAQLQ and ED visits were collected at baseline, and approximately 6 months and 12 months after enrollment. As an initial exploratory analyses of our primary outcome measures, we performed a repeated measures analysis using a general linear mixed model (LMM) for the continuous variables (ACT™ and MiniAQLQ) and a logistic regression using a generalized estimating equation (GEE) for categorical data (ED visits) to examine change over time. These models assume an intent-to-treat analysis. The LMM and GEE models include all available observations in the analyses and assume the data are missing at random, applying the restricted maximum likelihood estimation method. For the repeated measures analyses, we included time, study group, and the interaction between time and study group. The slopes between baseline and 6 months and 6 months and exit were calculated for each treatment group. The difference between treatment groups was compared at each time point. For the ACT™ and MiniAQLQ scores, the LMM was used to compute the difference in means and 95% confidence intervals (Cls) for effect size between the two treatment groups between baseline and exit. The logistic regression model was used to estimate the odds of having at least one ED visit in the 12-month period before exit compared with the 12-month period before baseline. The model was used to compute the odds ratio (OR) and 95% CIs for the effect size between the two treatment groups between baseline and exit.

We also performed exploratory analyses of potential predictor variables. Independent

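### The primary ACT and MiniAQLQ test uses only participants with an exit score, while the mixed model that would use the non-completers' earlier data is ranked exploratory

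*SAP*

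**What the plan says.** The SAP, Statistical Analysis, under Primary Outcome Analyses, states: "The initial analysis of the outcome measures used an independent, two-sample, two-sided t-test, assuming equal variances", and sets the time point as study exit. Its only missing-data rules concern unanswered questionnaire items: no ACT score if any item is missing, and worst-score replacement for up to two MiniAQLQ items. Nothing covers a participant with no exit visit. The same section gives 193 completers and 71 non-completers and compares their baseline data.

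Under Exploratory Analyses the SAP fits a linear mixed model (LMM) to ACT and MiniAQLQ and a GEE logistic model to ED visits: "The LMM and GEE models include all available observations in the analyses and assume the data are missing at random". Intention-to-treat is mentioned only there.

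The protocol's analysis plan (Section G) says: "All analyses will be performed according to treatment assignment, and all available data will be included in the evaluations". The sentence goes on to tie this to participants who stop the assigned treatment, and calls it modified intention-to-treat. The plan names t-tests for bivariate associations and linear or logistic regression with GEE variance for group differences, and it makes the unadjusted analysis primary.

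On month-6 data the documents differ. Protocol Section F2 lists ACT and healthcare utilization for the month-6 call. The SAP says MiniAQLQ was also collected at about 6 months.

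**The concern.** A comparison of exit means uses only people who have an exit score. If the link between asthma control and dropping out differs by arm, the two groups of completers are selected differently and their difference in means is biased even when treatment does nothing.

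The design makes this plausible. Intervention participants receive a home assessment, four further home visits and tools worth up to $350 per home. Controls receive calls, and qualify for the home intervention and tools only if they complete the study (protocol Sections F2 and L). The SAP's baseline comparison of completers with non-completers would not reveal the problem, because it does not look at control during the study and is not stated to be done by arm.

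The month-6 ACT is the natural protection. It was collected in both arms by callers who, according to the SAP's Randomization section, were blinded. The headline test ignores it, and the model that uses it is reported below the headline as exploratory.

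**Working it through.** **1. The plan's own figures.** 300 × 0.65 / 2 = 97.5, against 97 per arm stated.
- ACT: SE = 4 × √(2/97) = 0.574; 3/0.574 = 5.22; power = Φ(5.22 − 1.96) = 99.9%. Stated: above 99%.
- MiniAQLQ: SE = 0.6 × √(2/97) = 0.0862; 0.5/0.0862 = 5.80; power above 99.9%. The protocol states above 99% and the SAP roughly 99%.

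Both reproduce. The 193 completers compare with 2 × 97 = 194 planned, and the loss of 71/264 = 26.9% is below the planned 35%. Power is intact, so the issue is bias.

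**2. Inputs for the bias.** From the documents: ACT SD 4 and 26.9% lost. Assumed, because the documents do not give them: 132 per arm, correlation ρ of 0.5 to 0.6 between any two visits, no treatment effect, and a probit dropout model on month-6 ACT with slope b of 0.25 to 1 per SD.

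**3. Bias of the completer difference, dependence in one arm only.** The proportion staying is 193/264 = 0.731, with normal quantile 0.616 and density 0.330 at that point. The mean shift factor is 0.330/0.731 = 0.451.

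Bias = 4 × ρ × [b/√(1+b²)] × 0.451

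SE of the completer difference = 4 × √(2/96.5) = 0.576. Null rejection ≈ Φ(bias/SE − 1.96) + Φ(−bias/SE − 1.96).

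| b per SD | b/√(1+b²) | Bias, ρ = 0.5 | Bias, ρ = 0.6 | Approx. null rejection |
|---|---|---|---|---|
| 0.25 | 0.243 | 0.22 | 0.26 | 7% |
| 0.5 | 0.447 | 0.40 | 0.48 | 11% to 13% |
| 1 | 0.707 | 0.64 | 0.77 | 20% to 26% |

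Simulation under the same assumptions agrees: bias of about 0.2 to 0.8 points, with rejection of 6% to 28%.

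**4. Other patterns.**
- *Opposite directions in the two arms, b = 0.5 in each:* the bias doubles to 2 × 0.40 = 0.81 (before rounding) up to 2 × 0.48 = 0.97. Rejection is 28% to 40% in simulation. Steeper opposite slopes would give more.
- *Same dependence in both arms:* the two shifts cancel. Bias is about 0 and rejection about 5%.

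**5. What the mixed model does.**
- *Every leaver gave a month-6 ACT:* dropout depends only on observed data, and the likelihood estimate has bias of about 0 in simulation, with similar spread.
- *Leavers went before month 6:* only baseline can be conditioned on. To first order the remaining share of the bias is (ρ − ρ²)/ρ = 1 − ρ, which is 50% at ρ = 0.5 and 40% at ρ = 0.6. In points this runs from about 0.5 × 0.22 = 0.11 to 0.5 × 0.64 = 0.32.

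**6. Not calculated.** No dropout simulation was run for MiniAQLQ. If it was not taken at month 6, its non-completers are always in the second case of step 5.

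**The case against.** The strongest reply is that an exit comparison among those followed was foreseen. Both documents base power on 97 per arm remaining, and the SAP's power section names the equal-variance t-test. That is true. It settles power, not bias.

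A reader might infer that the SAP contradicts the protocol's all-available-data rule. The documents do not support that. The rule is tied to stopping treatment and is called modified intention-to-treat, so it can mean all available exit data by assigned arm, which the t-test uses. An unadjusted regression of exit score on arm would give the same mean difference on the same people. The protocol mentions longitudinal models only for healthcare utilization. What stands is that the SAP is not clearly consistent with the protocol's all-available-data and regression/GEE wording, and that it does not explain the choice.

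A reader might also infer that any link between dropout and outcome biases the t-test. Under no effect it does not, if the link is the same in both arms. Differential dropout is needed, and the documents give no dropout counts, reasons or timing by arm.

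The size depends on an assumed slope. At the weak end it is small, and even 0.8 points is well below the 3-point ACT minimal clinically important difference. The SAP also already reports the mixed model with confidence intervals, so much of the dispute is about which result leads.

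Finally, the SAP is dated 9/9/2018 and written in the past tense. Changing the primary analysis now may be a change made with results known. That objection stands and shapes the fix.

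**Conclusion.** The concern holds in limited form. The primary ACT and MiniAQLQ comparison excludes everyone without an exit score, has no rule for a missing exit visit, and leaves month-6 ACT unused, while a better-protected model sits below it as exploratory. The 26.9% assumes that 193 + 71 = 264 is everyone randomised. Neither document prints that total or its split by arm, nor says that none of the 71 had any exit data.

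Under the stated assumptions, dropout tied to month-6 ACT in one arm biases the ACT difference by about 0.2 to 0.8 points and raises null rejection from 5% to about 6% to 28%. Moderate dependence in opposite directions raises it to about 28% to 40%. These figures show what could happen. They are not evidence that this trial's result is biased.

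The mixed model is a partial remedy: nearly complete for leavers with a month-6 ACT, and about half to 60% effective for those who left earlier. The support is firmest for ACT. For MiniAQLQ it depends on whether a month-6 score exists. It does not carry over to ED visits: the SAP attributes missing-at-random validity to its GEE model too, but unweighted GEE does not give that protection.

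**What to change.** - Make the LMM between-group contrast at exit, with 95% CI and p-value, the primary estimate for ACT and MiniAQLQ. Name the covariance structure, which the SAP leaves open; the likelihood estimate in the calculation corresponds to an unstructured one.
- Keep the exit t-test on completers as a labelled sensitivity analysis.
- Beside each result, give the number randomised and the number analysed by arm.
- Reconcile protocol Section F2 with the SAP's Exploratory Analyses on whether MiniAQLQ was taken at month 6. If it was not, say that the LMM protects MiniAQLQ only through baseline.
- State the date and reason for the change, whether results were known by then, and how the analysis relates to the protocol's all-available-data wording.
- Do not promote the unweighted GEE for ED visits on the same argument.

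The model is already planned, so the work is wording, reporting order and a table of numbers by arm. There are two costs. The headline then depends on a model rather than a two-sample test. And because the SAP reads as a record of completed work, the change must be presented openly as a late one, with both results shown.

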# THE HOUSTON HOME-BASED INTEGRATED INTERVENTION TARGETING BETTER ASTHMA CONTROL (HIITBAC) FOR AFRICAN AMERICANS

#### Statistical Analysis Plan

### Revision Dated 9/9/2018

## Power and Sample Size

Power and sample size calculations were performed using the PS program of Dupont and Plummer. The study was initially designed to recruit 300 patients in total. Based on the literature and our previous experience with the targeted participant population, we estimated a 35% LTF rate, resulting in 97 patients per group at the end of the study.

The primary outcome measures were the ACT™ score, MiniAQLQ score, and self-reported ED visits. For the ACT™ score, assuming a standard deviation of 4, a sample size of 97 participants per group gave greater than 99% power to detect a minimal clinically important difference (MCID)—which has been determined to be 3 for the ACT™ score—at the significance level of 0.05 (2-sided) using an independent, two-sample t-test assuming equal variances. For the MiniAQLQ score, assuming a standard deviation of 0.6, a sample size of 97 participants per group provided roughly 99% power to detect a MCID—which has been determined to be 0.5 for the MiniAQLQ score—at a significance level of 0.05 (2-sided) using an independent, two-sample t-test assuming equal variances. For ED visits, assuming a standard deviation of 3 for the number of self-reported ED visits for asthma over the previous 12 months, a sample size of 97 per group provided about 90% power to detect a difference of 1.4 in annual ED visits between the two groups at the significance level of 0.05 (2-sided) using an independent, two-sample t-test assuming equal variances.

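### An undefined normality check can lead ACT and MiniAQLQ to an unnamed rank or transformed analysis, and the SAP does not say which result is primary

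*SAP*

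**What the plan says.** The SAP lists three primary outcomes: "The primary outcome measures were the ACT™ score, MiniAQLQ score, and self-reported ED visits". Under Statistical Analysis, an equal-variance two-sample t-test on exit values is labelled the initial analysis of all three. An F test of the variances can bring in Welch's version as an alternative.

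Normality is then assessed with graphs, two shape statistics and the Shapiro-Wilk test, and departures from "normality were addressed by using nonparametric analytic methods or data transformation". There is no cut-off, no statement of which tool governs, no named rank test or transformation for ACT and MiniAQLQ, and no rule for choosing between the two routes. The SAP does not say whether the t-test or its alternative is then the primary result.

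The effect measure for ACT and MiniAQLQ is fixed without reference to that check: "we calculated the raw mean difference (MD) for the continuous variables". For ED visits the rank-sum and Fisher tests are run alongside the t-test in every case, so the check does not decide whether they appear.

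The protocol's data analysis plan (Section G) relies on t-tests and regression for between-group comparisons and takes the unadjusted analysis as primary. It has no normality-based switch for these comparisons.

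**The concern.** The trial's question for ACT and MiniAQLQ is about means: the important differences are mean differences and the power is that of a t-test. A rank-sum test asks whether scores in one arm tend to exceed those in the other. A test on a log scale compares means of logs. If either supplies the p-value while the raw mean difference supplies the estimate, the two can point different ways, and the SAP does not say which governs.

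The second issue is freedom of choice. When several analyses are allowed and none is designated, the analyst can select among them after seeing the data. That can raise the false-positive rate above the stated level ("All hypothesis tests were two-sided and assessed at the 0.05 level of significance").

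**Working it through.** **Inputs.** From the SAP, Power and Sample Size: "The study was initially designed to recruit 300 patients in total"; "we estimated a 35% LTF rate, resulting in 97 patients per group at the end of the study"; for ACT, "assuming a standard deviation of 4, a sample size of 97 participants per group gave greater than 99% power" to detect a difference "which has been determined to be 3 for the ACT™ score". For MiniAQLQ the SD is 0.6 and the difference 0.5.

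**The plan's own figures.** 300 × 0.65 / 2 = 97.5, stated as 97. Power ≈ Φ(δ / (SD × √(2/n)) − 1.96), with √(2/97) = 0.1436.
- ACT: 3 / (4 × 0.1436) = 5.22; 5.22 − 1.96 = 3.26; power 99.94%.
- MiniAQLQ: 0.5 / (0.6 × 0.1436) = 5.80; 5.80 − 1.96 = 3.84; power 99.99%.

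Both agree with the SAP. They are calculations for a test of means on the raw scale.

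**Type I error by simulation.** The main assumptions, none of them in the documents, are: ACT as a rounded normal score with SD 4, limited to 5-25, with the same mean (15 to 20) in both arms; 97 per arm; Shapiro-Wilk at 0.05 as the sole trigger; rank-sum as the nonparametric test; log(x+1) or log(26−x) as the transformation. With 4,000 trials per setting, the Monte Carlo standard error at 5% is √(0.05 × 0.95 / 4000) = 0.34 percentage points. The ranges cover several means and runs that differ in trigger (pooled residuals or each arm) and transformation.

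| Procedure | False-positive rate at nominal 5% |
|---|---|
| t-test fixed in advance | 4.9-5.2% |
| Mechanical switch to rank-sum when the check fails | 4.5-5.6% |
| Check fails, then smaller p of rank and log tests | 5.6-7.1% |
| Check fails, then smallest p of t, rank and log tests | 5.8-7.6% |

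In the last two rows the lower values belong to means where the check seldom fails. Shapiro-Wilk rejected in at least one arm in about 18%, 33%, 98% and 100% of trials at means 15, 17, 19 and 20. The higher rates come from scores piling up at the assumed ceiling of 25.

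**Is the switch needed?** Across normal, ACT-like, lognormal and negative binomial data, including equal means with unequal SDs, the fixed t or Welch test rejected in 4.4-5.4% of null trials. At about 97 per arm the test of means does not need the protection.

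**Can the p-value and the estimate separate?** An illustration with count data: negative binomial, mean 1.5 in both arms, SD 3 against 2. The t-test rejected in 5.4% of trials and the rank-sum test in 44.5%. The distributions do differ here, so the rank test is not wrong. It answers another question, and a raw mean difference near zero would stand beside a small p-value. The example is deliberately marked and is not a forecast for ACT or MiniAQLQ.

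**The case against.** The strongest reply is that nothing is replaced. The t-test is only the initial analysis, Welch is an alternative, the ED-visit rank test is an addition, and the raw mean difference is reported throughout. On that reading, rank or transformed results for ACT and MiniAQLQ are supplementary. This stands as a plausible reading. A reader might infer that the check swaps out the primary test, but the text never says so. What remains is that the SAP does not settle which result governs.

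A reader might also infer that testing for normality first inflates the error rate. The simulations do not support that: the mechanical switch stays at about 5%. The increase needs an analyst who takes the smallest p-value. The wording permits that, but nothing in the documents shows that it was done. Taking the smallest of the three p-values with no normality check at all gives 6.8-7.8%, but that is not the SAP's procedure, because alternatives open only after a departure.

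Finally, how often the check would fail is unknown. The documents give no exit distribution, and approximate normality judged with several tools need not follow a mild Shapiro-Wilk rejection. This also stands.

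**Conclusion.** The point holds as an ambiguity with a cheap remedy. The SAP leaves the primary result for ACT and MiniAQLQ undetermined once normality is doubted, while the important differences, the power and the reported effect remain on the mean scale. The possible cost in type I error is about 6-7% in place of 5%, and only under smallest-p selection. Under a fixed rule it is nil. These figures rest on the assumed ACT model; MiniAQLQ was not simulated. The practical weight is low, since the raw mean difference is reported in any case and the test of means is sound at this sample size.

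**What to change.** Name one mean-scale primary analysis for ACT and one for MiniAQLQ, to be used whatever the diagnostics show. The preferred choice is a linear model on the raw exit score with treatment group, baseline score, the randomization strata in the SAP (age and sex; protocol Section F1 lists age only) and robust standard errors. The minimum is Welch's t-test, which alone removes the switching problem and makes the F test of variances unnecessary. Label rank-based and transformed results as sensitivity analyses.

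The adjusted model must be reconciled with the protocol's statement that unadjusted results are primary. Welch's test raises no such conflict.

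The cost is SAP wording and, for the adjusted model, that reconciliation; no new data are needed. The downside is slightly less power than a rank test if scores are very skewed, which matters little against planned power of about 99.9%. The SAP is written in the past tense and already counts 193 completers and 71 non-completers, so the change would clarify reporting and could not protect prospectively. The report should say when the primary result was designated.

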PHONE CALLS AND STUDY-RELATED LETTERS Participants in both the control and intervention arms will receive a phone call at month 6 to assess asthma control (ACT) and healthcare utilization (see attachment, HIITBAC_6_PHONE-6MO-FU_20160512). Participants may also receive a letter to ask them to call in to complete their mid-year survey if that is more convenient for them or if we are having difficulty reaching them by phone (HIITBAC_6 LETTER-6MO-FU). Participants in the control arm are also called at months 3 and 9 to check in and to verify their current phone, address and other contact information (HIITBAC_6_PHONE-3-9MO-FU_20151009). As per standard of care, lab results (e.g., Total IgE and the Zone 6 allergen panel) will be mailed to the patients in both arms shortly after the results are posted in Epic. This correspondence

includes a letter explaining the results and invites participants to call our provider to discuss. Participants are also notified by phone and/or at a home visit, as appropriate. Participants also receive scheduling calls and mail/email/phone/text appointment and/or study reminders as appropriate and to aid in retention.

ENVIRONMENTAL HEALTH CLINIC: POST-INTERVENTION HEALTH ASSESSMENT The follow-up clinical assessment will occur approximately 12 months after the baseline clinic visit and obtain data similar to that collected during the baseline visit (see attachment, HIITBAC_4_EXIT-QUESTIONNAIRE_20151211), plus some questionnaires on participant behavior change during the study and participant satisfaction (HIITBAC_4_SATISFACTION_Q_20151211). Additional questions about the impact of Hurricane Harvey on the participant's health and well being were added in September 2017 (HIITBAC_4_EXIT-QUESTIONNAIRE_Harvey_Addendum). Self-administered questionnaires may be mailed to the participant just prior to their exit visit, if desired, in order to shorten the length of the exit visit. At this visit, the usual care group will be given the option of scheduling a home environmental assessment, and subsequent home-based intervention (up to two additional visits). As with the baseline visit, the post-intervention clinic visit will typically take place at the Harris Health Smith Clinic. It may also be conducted at Ben Taub, a community site (e.g., Casa de Amigos Health Center, a City of Houston Multi-Service Center), or the participant's home.

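### In the exploratory ED-visit model, within-arm slopes through month 6 cannot be read as change in ED use, because the look-back windows differ or overlap

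*SAP*

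**What the plan says.** SAP, Statistical Analysis, Exploratory Analyses, gives three collection times: "Data on ACT™, MiniAQLQ and ED visits were collected at baseline, and approximately 6 months and 12 months after enrollment". ED visits are analysed by "a logistic regression using a generalized estimating equation (GEE) for categorical data (ED visits) to examine change over time". The model terms are given for all outcomes together: "For the repeated measures analyses, we included time, study group, and the interaction between time and study group". Two outputs follow, also for all outcomes together: "The slopes between baseline and 6 months and 6 months and exit were calculated for each treatment group", and "The difference between treatment groups was compared at each time point". The section adds that both model types use every available observation.

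Two of the three ED windows are stated. In the primary analysis, "ED utilization was measured by the frequency of visits to an ED during the 12-month period prior to the exit visit". The ED-specific sentence of the exploratory section concerns the "odds of having at least one ED visit in the 12-month period before exit compared with the 12-month period before baseline". So baseline and exit each look back 12 months.

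The third window is not stated. Protocol F2 says only that participants in both arms "will receive a phone call at month 6 to assess asthma control (ACT) and healthcare utilization". It refers to a month-6 phone form, which is not among the documents.

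**The concern.** Any visit versus none depends on how long the person is asked to look back. A model that treats three such reports as one outcome at three times needs windows of equal length that do not overlap. Here the outer two windows are 12 months each, and only 6 months separate month 6 from either of them. A 6-month look-back at month 6 has a different length. A 12-month look-back overlaps both neighbours. In either case months 0 to 6 are counted again at exit.

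What is at stake is the reading of the time course. ED visits are one of three primary outcome measures, and this model is meant to show how they changed. A reader shown the slopes could infer early benefit that was then lost, or slow onset, when neither took place.

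**Working it through.** **The plan's own ED figure.** SAP, Power and Sample Size: 97 per group, difference 1.4, SD 3, two-sided 0.05, t-test, about 90% power. The noncentral t gives 0.899, so the figure reproduces. It belongs to the primary exit comparison. No figure is stated for the exploratory model.

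**Inputs.** The annual SD of 3 is from the SAP. The mean rate is in neither document, so 1 and 2 visits a year are assumed. Each person's underlying rate is held constant over time unless a treatment effect is stated.

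**Formulas.** For a mean count m in a window, P(at least one visit) is:
- Poisson: 1 − exp(−m)
- Negative binomial: 1 − (1 + m/k)^(−k), where k = μ²/(9 − μ) makes the annual variance 9 at annual mean μ. This gives k = 0.125 at μ = 1 and 0.571 at μ = 2.

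**Case A: 6-month look-back at month 6, no true change.** The mean is μ at baseline and exit and μ/2 at month 6.

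| Model | μ | P, 12 months | P, 6 months | OR, baseline to month 6 | OR, month 6 to exit |
|---|---|---|---|---|---|
| Poisson | 1 | 0.632 | 0.393 | 0.38 | 2.65 |
| Poisson | 2 | 0.865 | 0.632 | 0.27 | 3.72 |
| Negative binomial | 1 | 0.240 | 0.182 | 0.71 | 1.42 |
| Negative binomial | 2 | 0.577 | 0.439 | 0.57 | 1.74 |

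First row: odds at 6 months 0.393/0.607 = 0.649; odds at 12 months 0.632/0.368 = 1.718; ratio 0.38; inverse 2.65. The whole fall and the whole rebound come from the window.

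**Case B: 12-month look-back at month 6.** All three windows have length 12, so a constant rate gives equal probabilities and slopes of zero. Now let the intervention multiply the rate by 0.6 from randomisation onward (assumed), with μ = 1. The month-6 window covers 6 months before and 6 months after randomisation, so its intervention-arm mean is 0.5 + 0.5 × 0.6 = 0.8. At exit the mean is 0.6. The control mean is 1 throughout.

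| Model | Arm OR at month 6 | Arm OR at exit | Intervention arm, month 6 to exit |
|---|---|---|---|
| Poisson | 0.71 | 0.48 | 0.48/0.71 = 0.67 |
| Negative binomial | 0.90 | 0.78 | 0.78/0.90 = 0.86 |

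Because the control probability does not change, the month-6 arm OR is also the intervention arm's baseline-to-month-6 slope. An effect that is complete on day one is therefore displayed as two steps of similar size, 0.71 then 0.67 (or 0.90 then 0.86).

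**The comparison between arms at month 6.** With no effect, both arms have the same probability under either window, so the odds ratio is 1.00. A three-time logistic GEE was simulated with no effect (97 per arm, 400 runs per window, rate 1, negative binomial with k = 0.5). It rejected at nominal 0.05 as follows:
- time-by-group term at month 6: 0.0475 (6-month window) and 0.040 (12-month window)
- arm comparison at month 6: 0.025 and 0.0225

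Neither is inflated.

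**The case against.** The strongest reply has four parts.

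1. **The month-6 window is unseen.** It may be fixed in the phone form, and the fall and rebound arise only if that form asks about 6 months. This stands, and the odds ratios in case A are conditional on it. It does not rescue the slopes, because the 12-month alternative has its own fault.
2. **ED slopes may never have been produced.** The slopes sentence covers all the repeated-measures outcomes, while the ED-specific sentences describe only baseline against exit. The general text is also loose: it lists MiniAQLQ at 6 months, whereas the protocol's month-6 call names only ACT and healthcare utilization. This stands as a doubt. Yet the SAP lists ED visits among the month-6 data and says that all available observations enter the model. If month-6 ED data were left out, the text should say so.
3. **Randomised arms share the window.** A reader might infer that the month-6 arm comparison is an artefact too. The documents do not support that. With a 6-month look-back it is a valid comparison of months 0 to 6, on a different scale from exit. With 12 months it is diluted by time before randomisation, and dilution needs a real effect to act on.
4. **The overlap may not harm inference.** Shared months affect the within-person correlation, but GEE estimates with robust variance tolerate a wrong working correlation. No harm from this was shown, and the point does not rest on it.

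**Conclusion.** The concern holds for the within-arm ED slopes through month 6. With a 6-month look-back they are mechanical: an odds ratio of about 0.27 to 0.38 (Poisson) or 0.57 to 0.71 (negative binomial) down to month 6, and the inverse back up to exit, with no true change. With a 12-month look-back they are not created by the window, but they weaken and mistime a real effect. The sizes rest on assumed rates of 1 to 2 visits a year, a steady rate within person, and the SAP's SD of 3 for the negative binomial figures. The direction needs only that the look-back is 6 or 12 months.

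A reader might go further and infer that the trial's ED result is compromised. It is not. The primary analysis compares arms at exit, and the stated exploratory odds ratio sets 12 months against 12 months. The one blemish is that Protocol F2 allows exit up to 6 weeks early, so a few exit windows may reach back before baseline. Severity is minor: one exploratory analysis is affected.

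**What to change.** - Fit the ED GEE to baseline and exit only. This keeps the odds ratio that the SAP already describes.
- Drop the ED slopes through month 6, and say in the SAP that the slopes sentence applies to the other outcomes.
- State the month-6 look-back. If it is 6 months, report the month-6 arm comparison separately, as an outcome over months 0 to 6.
- Use months 0 to 6 and 6 to 12 in a count model with a log-exposure offset only if visits can be dated. Neither document shows that self-reported visits were.

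The cost is a few lines of SAP text and a refit on a restricted data set, with no new data. The downside is that no ED trajectory through month 6 can be shown.
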